1. PROJECT TITLE

Studying the Effectiveness of Non-Invasive Glucose Sensors in Patients with Diabetes: The SENSOR Study

4. ESTIMATED DURATION OF THE STUDY

1 year

5. LAY LANGUAGE SUMMARY OR SYNOPSIS (no more than one paragraph)

Self-testing of glucose by patients involves needles, which can cause discomfort or inconvenience; these and other factors can lead to decreased willingness to perform these checks that are vital to diabetes management. While technology has evolved, we currently do not have available a glucose monitoring device that is needle-free. We are studying a glucose sensor that adheres to the skin, similarly to a temporary tattoo. This sensor has not yet been tested in individuals with diabetes, and we will examine its accuracy and acceptability in these patients. Results from this clinical trial could serve as the basis for further development of a non-invasive, wearable glucose sensor that can provide measurements of glucose levels continuously.

6. SPECIFIC AIMS

Specific Aim 1: To gather initial data to permit a future assessment of the feasibility, accuracy, reliability, and validity of a wearable glucose sensor, compared with SMBG, in patients with DM.

Specific Aim 2: To evaluate whether patients with DM will find this sensor to be acceptable to use.

7. BACKGROUND AND SIGNIFICANCE

Self-monitoring of blood glucose (SMBG) can both facilitate and hinder adherence in patients with diabetes mellitus (DM). Readings are crucial to successfully managing this disease, as they provide real-time information on hypoglycemic and hyperglycemic excursions. SMBG can also help guide titration of medications, and can encourage patient engagement.¹ There is a correlation between increased frequency of SMBG and more optimal hemoglobin A1c (HbA1c) in type 1 DM (T1DM) and type 2 DM (T2DM) patients.^{2,3,4} There are drawbacks. Patients may find piercing the skin to check glucose up to several times a day uncomfortable and obtrusive.⁵ SMBG offers only a snapshot of the patient's glucose at the time of testing.

Continuous glucose monitoring (CGM) can reveal glucose trends. A subcutaneous sensor transmits interstitial glucose readings approximately every five minutes. Yet, sensor insertion requires a needle.⁶ Patients still must test SMBG about 4 times per day to calibrate the sensor.⁶ CGM is less accurate with low or rapidly rising glucose. A non-invasive glucose monitor, the GlucoWatch, was discontinued due to problems with accuracy and tolerability.

Compounding these challenges is the surging number of individuals with DM. Every 19 seconds, an American 20 years of age or older is diagnosed with DM.⁷ Patients with T2DM have a 2- to 4-fold increased risk of cardiovascular disease, stroke, and peripheral vascular disease compared with non-diabetic individuals.⁸ Diabetes is the leading cause of blindness, non-traumatic lower-limb amputation, and renal failure in the US.⁹ The total costs of diagnosed DM in the US in 2012 were \$245 billion, an increase of 41% from 2007.¹⁰ If current trends continue, by 2050, 1 in 3 Americans could have DM.¹¹ Greater patient engagement with glucose monitoring can potentially lead to reduced risk of complications of diabetes, improved outcomes, and enhanced quality of life.

There is thus an unmet need for a non-invasive glucose monitoring device. UCSD nanoengineers developed a flexible, ultra-thin sensor adherent to the skin, similar to a temporary tattoo.¹² Preliminary data from seven individuals without DM demonstrated correlation between glucose measurements from this sensor and a glucometer.¹² This proposed study would be the first to examine this sensor in individuals with DM, and would serve as the basis for future development of a continuous, non-invasive sensor. We hypothesize that compared with a glucometer, a tattoo sensor can accurately measure glucose in patients with DM.

8. PROGRESS REPORT

Not applicable

9. RESEARCH DESIGN AND METHODS

We will enroll in this pilot clinical study a total of up to 50 patients between the ages of 18-75 with diabetes of any type, including type 1 diabetes mellitus (T1DM), type 2 diabetes mellitus (T2DM), or diabetes secondary to etiologies such as pancreatitis; or to medications, such as steroids: defined as having a fasting plasma glucose (FPG) ≥ 126 mg/dL, or hemoglobin A1c (HbA1c) $\geq 6.5\%$. Participants will wear a tattoo sensor placed by study staff on one to three visits, on up to three different days (participants can elect to perform all measurements on one day), at various times: 1) fasting (before breakfast), 2) at least 1 time point between 15 to 200 minutes after consuming a meal, and 3) during and 4) 15 minutes after exercising aerobically for 15-30 minutes (walking at a moderate pace, or pedaling on a stationary bicycle, at up to 80% of maximum heart rate). Participants will warm up for 5 minutes before exercising and cool down for 5 minutes after completing the exercise session. We will obtain at least three sensor readings from each of these four time points, for a minimum total of 12 sensor readings. (We will compare participants' glucose levels as detected by a tattoo sensor, with at least 3 corresponding simultaneous fingerstick glucose readings, (measured by a glucometer, used as standard of care for those with diabetes). There will be a minimum of 12 glucometer readings, one for each of the above times. The total number of sensor and glucometer readings combined will be at least 24. We will monitor for acceptability and any discomfort through both verbal feedback and a brief, written questionnaire. Participants will be informed of their sensor and glucometer data. We will advise participants that only the glucose readings from the glucometer are non-experimental, and are considered accurate.

Participants can elect to perform exercise on a stationary bicycle; this portion of the study will be done at either the UCSD Clinical and Translational Research Institute's Center for Clinical Research, or the UCSD Exercise and Physical Activity Resource Center (EPARC). Those who are unable to or prefer not to exercise on a stationary bicycle, can choose to walk at either the UCSD Clinical and Translational Research Institute's Center for Clinical Research, or if a UCSD SBHP inpatient, at the UCSD Hillcrest Senior Behavioral Health Program (SBHP) Inpatient Unit. Study staff will monitor all participants during and after all exercise sessions.

All of the sensor components are printed onto temporary tattoo paper; the sensors are self-adhesive and are disposable. By applying a mild electrical current to the epidermis, sodium ions, and in turn, interstitial fluid glucose molecules, migrate toward an electrode. This process is termed reverse iontophoresis. An electrochemical sensor that is part of the tattoo detects the electrical charge strength of glucose to measure the glucose level.^{12,13}

Prior *in vitro* and *in vivo* research conducted in the laboratory setting on human participants has demonstrated the efficacy of these sensors.¹² This work was conducted in the laboratory of [name]. However, these sensors have not been validated in a clinical population previously. We will conduct this study in both outpatient and inpatient settings: the UCSD Clinical and Translational Research Institute's Center for Clinical Research, and the UCSD Senior Behavioral Health Program (SBHP), respectively. Individuals from this population may have conditions, such as depression, that may hamper their self-management of their diabetes. The inpatient setting offers the ability to simultaneously monitor other factors like dietary intake, degree of physical activity, and medication use. We can measure these parameters more precisely, as these are regularly and closely monitored and documented by nursing staff or other individuals. As many patients do not usually record such data as extensively, this information is more accurate than patient recall. In order to validate sensor use, mapping these covariates is essential, and the inpatient setting will allow us to measure these parameters efficiently, and without additional cost. Since one of the study sites is the UCSD geriatric psychiatry inpatient unit (the UCSD Senior Behavioral Health Program Inpatient Unit), some patients will have comorbid psychiatric diagnosis. We will not recruit any patients with cognitive impairment, to ensure that all participants have the ability to provide informed consent.

Since this is a pilot, single-arm study that is collecting preliminary data, we will use simple descriptive statistics to assess the glucose readings. The number of participants anticipated for enrollment is thus not based on statistical power analysis.

Sensor and glucometer values will be analyzed to determine the extent that these correlate in patients with diabetes; we will determine measures such as the mean, median, and standard deviation at the different time intervals.

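### Does the plan ask for 4 or 12 fingerstick reference readings per participant?

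*Combined protocol and SAP*

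**What the plan says.** All the relevant text is in Section 9 of the combined protocol and SAP. The measurement occasions are given as a numbered list: "at various times: 1) fasting (before breakfast), 2) at least 1 time point between 15 to 200 minutes after consuming a meal, and 3) during" exercise, with a fourth item 15 minutes after exercise. The sensor requirement is "We will obtain at least three sensor readings from each of these four time points, for a minimum total of 12 sensor readings". These are to be compared "with at least 3 corresponding simultaneous fingerstick glucose readings". Then come the two sentences at issue: "There will be a minimum of 12 glucometer readings, one for each of the above times", and "The total number of sensor and glucometer readings combined will be at least 24".

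Later in the same section the analysis is described: "Sensor and glucometer values will be analyzed to determine the extent that these correlate in patients with diabetes", together with means, medians and standard deviations at the different intervals. On sample size it says: "The number of participants anticipated for enrollment is thus not based on statistical power analysis". No other section states how many fingersticks are taken at each time.

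**The concern.** The section uses the word times for the four numbered occasions and then counts them as four time points. On that usage, the closing clause of the glucometer sentence gives 4 readings, yet the same sentence says 12. The phrase before it asks for at least 3 fingersticks but does not say whether that is per time point, per visit or in total, so it does not settle the count by itself.

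The fingerstick is the reference measurement. Aim 1 (Section 6) and the accuracy hypothesis (Section 7) both rest on comparing the sensor with it. If only one were taken per time point, most sensor readings would have no simultaneous reference of their own, and the plan does not say how one fingerstick would be matched to three sensor readings. The count also sets the number of skin punctures, which Section 14 lists as a source of slight pain and slight infection risk.

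**Working it through.** **Inputs, all from Section 9.** Time points: 4. Sensor readings per time point: at least 3. Stated minimums: 12 sensor, 12 glucometer, 24 combined.

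**Sensor total.** 4 × 3 = 12, as stated.

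**Glucometer total, by possible reading of the text.** Combined total = 12 sensor readings + glucometer readings.

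| Reading | Glucometer | Combined | Matches 12 and 24? |
|---|---|---|---|
| Three per time point | 4 × 3 = 12 | 12 + 12 = 24 | Yes |
| One per sensor reading | 12 × 1 = 12 | 12 + 12 = 24 | Yes |
| One per time point (literal clause) | 4 × 1 = 4 | 12 + 4 = 16 | No |
| Three in total | 3 | 12 + 3 = 15 | No |

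The first two rows give the same minimum: three fingersticks at each time, each taken with one sensor reading. They reproduce both stated figures exactly.

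**Could extra post-meal times rescue the literal clause?** The post-meal item is open-ended ("at least 1 time point between 15 to 200 minutes after consuming a meal"). With n post-meal times and three other times, one fingerstick each reaches 12 when 3 + n = 12, so n = 9. Three sensor readings at each of 12 times would then be 36, and the combined total 36 + 12 = 48. Neither fits the stated 12 sensor readings or 24 combined, so this route fails.

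**Size of the gap if the clause were followed literally.** Glucometer readings would fall short of the stated minimum by 12 − 4 = 8 per participant, leaving 8/12 = 67% of the minimum sensor readings without their own reference. Getting there means ignoring the 12 in the same sentence and the 24 in the next.

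**The case for a change.** The best argument for a change is that this sentence is the collection instruction for the reference measurement, and that making it agree with itself costs one line. Its usage of times is fixed by the list above it, so a reader must override that usage to make the sentence work. Data are collected in both outpatient and inpatient settings, so two teams could read it differently, and there is no separate pairing rule to fall back on.

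The point about wording stands: the clause is imprecise, and neither redaction nor text extraction explains it. The predicted harm does not follow. A team that took 4 fingersticks would miss two explicit numerical minimums, and those minimums are the clearest part of the instruction. The requirement for at least 3 fingersticks comes directly after the requirement for three sensor readings per time point, and is most naturally read on the same basis. The pairing question arises only if a single fingerstick is taken. At the stated totals, the requirement that fingersticks be corresponding and simultaneous already ties each one to a sensor reading.

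**Conclusion.** The inconsistency is real but clerical. The clause implies 4 glucometer readings (16 combined), while the stated minimums are 12 and 24. Those minimums agree with each other and with three simultaneous fingersticks at each of four time points. A team meeting them collects the 12 reference readings that the comparison needs.

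Little else depends on the clause. The study is a single-arm pilot with descriptive analysis. The number of pairs enters no power calculation, hypothesis test or decision rule. Correcting the phrase would leave every stated figure and every planned summary as it is. Restating the totals as 4 and 16 would have no support in the text, since both totals contradict it.

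The conclusion assumes that staff treat the two numerical minimums as binding and take the fingersticks alongside the sensor readings, as Section 9 asks. On that basis the expected loss of reference data is nil and no change to the plan is needed.

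### The hypothesis is accuracy against a glucometer, but correlation is the only between-device analysis named; paired differences should be the main accuracy summary

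*Combined protocol and SAP*

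**What the plan says.** **What is promised.** The synopsis (section 5) states: "we will examine its accuracy and acceptability in these patients". Section 7 closes with the hypothesis: "We hypothesize that compared with a glucometer, a tattoo sensor can accurately measure glucose in patients with DM". Aim 1 in section 6 is more cautious: "To gather initial data to permit a future assessment of the feasibility, accuracy, reliability, and validity of a wearable glucose sensor".

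**What was already known.** Section 7 reports the earlier result as a correlation: "Preliminary data from seven individuals without DM demonstrated correlation between glucose measurements from this sensor and a glucometer".

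**What is analysed.** Section 9 says: "Sensor and glucometer values will be analyzed to determine the extent that these correlate in patients with diabetes". The same sentence adds an open list of summaries (mean, median, standard deviation) by time interval, without saying whether they are of each device's readings or of paired differences. Earlier, section 9 says the two devices will be compared but names no statistic. Bias, limits of agreement, relative error and an accuracy criterion appear nowhere.

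**What is collected.** Each of four time points has at least three sensor readings, set against "at least 3 corresponding simultaneous fingerstick glucose readings". The text continues: "There will be a minimum of 12 glucometer readings, one for each of the above times". Then: "The total number of sensor and glucometer readings combined will be at least 24".

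**The concern.** The plan moves from a preliminary correlation, seen in seven people without diabetes, to a hypothesis of accuracy in people with diabetes, and then names correlation again as the analysis. Correlation measures how closely two sets of values follow a straight line. It does not measure how far one value lies from the other. A sensor could read far from the glucometer at every point and still give a high coefficient. Section 9 also mixes fasting, post-meal and exercise readings across all types of diabetes; that widens the glucose range and can raise the coefficient with no gain in accuracy.

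Section 7 intends the results to be the basis for developing a continuous sensor. Those developers will need to know how far off a reading is likely to be, and the one named between-device result would not tell them.

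**Working it through.** **1. The plan's own figure.** Four time points × 3 readings = 12 per device, and 12 + 12 = 24, which matches the stated minimum. One glucometer reading at each of the four times would give 4, and 12 + 4 = 16, which does not match. The totals therefore imply at least 12 pairs per participant, or 50 × 12 = 600 at full enrolment. The phrase about one reading for each time leaves the pairing rule unclear.

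**2. Inputs.** The documents give no glucose SD, sensor error or bias. The values below are assumptions: glucose mean 160 mg/dL, SD 50 (range 40 to 60), independent sensor error SD 15 mg/dL. The model is sensor = a + b × (glucose + error).

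**3. Offset and scaling.** For any a and any b > 0, r = SD / √(SD² + error SD²), and a and b cancel. At SD 50, r = 50 / √(2500 + 225) = 0.958. The difference has mean a + (b − 1) × 160 and SD √[((b − 1) × 50)² + (b × 15)²]. The 95% limits of agreement are the mean ± 1.96 SD. The mean absolute relative difference (MARD) comes from simulation with glucose kept within 50 to 400 mg/dL, where r is 0.954 in all three rows.

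| Sensor | r (formula) | Mean difference (mg/dL) | 95% limits (mg/dL) | MARD |
|---|---|---|---|---|
| Unbiased (a = 0, b = 1) | 0.958 | 0 | −29.4 to 29.4 | 8.2% |
| Reads 40 high (a = 40, b = 1) | 0.958 | 40 | 10.6 to 69.4 | 27.5% |
| Reads at 75% (a = 0, b = 0.75) | 0.958 | −40 | −73.0 to −7.0 | 25.1% |

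In the last row the SD of differences is √(12.5² + 11.25²) = 16.8, because the error is scaled along with the signal. If the error is instead held at 15 after scaling, r = 37.5 / √(37.5² + 15²) = 0.93 (0.92 in the simulation), so that row is then only approximately equal to the others. Over glucose SDs of 40 to 60 and several truncation ranges, the simulated r runs from 0.93 to 0.97. MARD stays at about 8%, 26% to 29%, and 25% for the three sensors.

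**4. Spread.** Take one unbiased sensor with error SD 22.36 mg/dL, so that its limits are ±1.96 × 22.36 = ±43.8 throughout. Then r = SD / √(SD² + 22.36²):

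| Glucose SD (mg/dL) | 25 | 30 | 40 | 50 | 60 |
|---|---|---|---|---|---|
| r | 0.75 | 0.80 | 0.87 | 0.91 | 0.94 |

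The two lower SDs might arise within a single time point, and the higher ones when time points are pooled. The sensor is equally accurate in every column.

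**5. Calibration, which bears on the fix.** Section 9 says the sensor detects the strength of an electrical charge. It does not say how that becomes mg/dL, or whether study fingersticks are used to calibrate it. Assume a common bias of +40, a participant offset SD of 15 and an error SD of 15 mg/dL.

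- Uncalibrated: bias 40; SD of differences √(15² + 15²) = 21.2.
- Offset fitted to the same 12 pairs used to judge the sensor: bias exactly 0; SD 15 × √(11/12) = 14.4; limits ±28.
- Offset fitted to the 3 fasting pairs and judged on the other 9: expected bias 0; SD 15 × √(1 + 1/3) = 17.3; limits ±34.

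Fitting and judging on the same fingersticks forces the bias to zero and makes the limits too narrow.

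**The case against.** The best defence is that Aim 1 promises only data for a later assessment of accuracy. Section 9 describes a single-arm pilot with simple descriptive statistics and no power analysis. On that reading, the accuracy claim rests on a lay synopsis and one background sentence, and rewording that sentence would cure the mismatch. The list of summaries is open, and the plan does say the devices will be compared. Means per device, if reported, would reveal an average bias such as +40 mg/dL. No sample size, decision rule or treatment choice depends on the statistic, participants are told that only glucometer values are considered accurate, and the retained pairs allow agreement to be calculated later.

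Most of this is fair, and it limits the harm. It does not remove the mismatch. The sentence in section 7 is the study's stated hypothesis, and section 5 says accuracy will be examined in this study. Means per device show average bias but not how widely individual readings differ; SDs per device cannot supply that. A general promise to compare names no statistic. Bias and limits of agreement are themselves descriptive, so they fit a pilot and need no power calculation. Naming them beforehand also removes the choice of the more flattering summary after the data are seen.

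It is also true that the documents do not say fingersticks are used for calibration. That point is a condition on the fix, not an error found in the plan.

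**Conclusion.** The concern holds and should be fixed. The plan hypothesises accuracy and names a between-device measure that cannot by itself show it. That correlation ignores a constant offset or positive rescaling is algebra and depends on no assumed value. The sizes do depend on assumptions: with r near 0.95 in each case, the mean absolute relative difference could be about 8% or about 25% to 28%; and one sensor with unchanged limits of agreement could show r from 0.75 to 0.94 as the glucose SD goes from 25 to 60 mg/dL. The consequence is a weak or misleading headline from a descriptive pilot. The data are not lost and no clinical decision is affected.

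**What to change.** Add a short paragraph to section 9 that does the following:

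- Makes the paired sensor-minus-glucometer difference the main accuracy summary: mean bias and 95% limits of agreement, overall and at each of the four time points, plus mean absolute relative difference. The percentage of readings within a pre-stated tolerance is optional.
- States that each sensor reading is paired with its simultaneous fingerstick, giving at least 12 pairs per participant, and reconciles the wording about one glucometer reading for each time.
- States that sensor values are in mg/dL and that the conversion is not fitted to the fingersticks used to judge agreement.
- Keeps correlation as a secondary summary and words conclusions in terms of agreement.

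If confidence intervals are given, they should allow for repeated pairs within a participant, for example by resampling participants. The present plan proposes no intervals, so this is guidance and not a fault.

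If the team does not want an accuracy analysis, the alternative is to restate the hypothesis as correlation only and bring the synopsis into line.

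The cost is a little more analysis and a headline that may look less favourable than a correlation coefficient. No new visits or patients are needed. If study fingersticks are used for calibration, those pairs must be left out of the agreement summary or a few extra fingersticks taken.
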